**Aim 1 and 2 Learning Collaborative Instrument.**

We will collect descriptive information about our partner agencies (e.g., rural region covered, agency type, caregiver services provided, etc.)

**Attach any unpublished instruments in the 'Other Study Documents' section of the Initial Review Submission Packet form after completing the study application. Published instruments should NOT be attached.**

**8.13 \* BIOSPECIMEN COLLECTION: Are you drawing any blood or collecting other biosamples (e.g. tissue, buccal swabs, urine, saliva, hair, etc.): (REQUIRED)**

Yes  No

**8.26 STATISTICAL METHODS: Briefly summarize the methods and types of analyses that will be performed:**

**Aim 1 Data Analysis Methods.**

**Descriptive analyses.** Caregiver and caregiver-reported partner socio-demographic characteristics, chronic conditions, and health utilization outcomes will be summarized as means ( $\pm$ SD), frequencies, percentages, and 95% confidence intervals at baseline and 1.5, 6, and 12 months. The distributions of covariates at baseline will be checked for balance between the two groups with histograms and/or boxplots.

**Primary analyses.** Primary analyses will compare caregiver stress (stress score) and depression symptoms (PHQ-8 score) between intervention and control groups over time with respective linear mixed effects models. Linear mixed effects models use all available observations in the data, assume data are missing at random, and provide an intention-to-treat analysis. Models will include group, time, and (group\*time) interaction terms as fixed effects and community organizations and subjects as random effects to account for the correlation within organizations and subjects due to measurements over time. Covariates with imbalanced distributions between the two groups will also be included in the models to control for potential confounding. The (group\*time) interaction term will be used to evaluate if the two groups differ in outcomes over time. The study is powered to allow 30% loss to follow up. To assess for potential differential withdrawal between groups, comparisons of withdrawal rates and time to withdrawal will be performed. Models based on a potential outcome framework will be used to assess treatment effect while accounting for noncompliance and missing data and to examine potential treatment mechanisms/pathways via intermediate variables (such as social support, self-efficacy, caregiving skills). Multiple imputation based on reasonable assumptions on mechanisms of missing data will be used to perform sensitivity analyses.

**Secondary analyses.** Secondary analyses will use (generalized) linear mixed effect models similar to the primary mixed effect models for continuous, categorical, and count secondary outcomes. Treatment effects in subgroups (e.g. by sex) of our interest will be evaluated using (generalized) linear mixed effect models with corresponding interactions of group, time and sex while controlling for false discovery rate. We expect a small and balanced recall error between the two groups but if recall error is unbalanced, measurement error models will be considered for treatment evaluation. We will examine loss to follow-up by comparing caregivers lost to follow-up to those who complete the study.

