Statistical Power Considerations in Building Better Caregiver Study

Study: R01 AG057855-01
PI: [name]
Date: 11 August 2019
NCT04428112

This document is a response to the DSMB recommendation: "The study team should provide a written explanation and revision to account for the changes in power calculations, particularly regarding drop-out rates."

Summary from study team. The statistical power consideration was revised based upon updated information on the challenges in the recruitment and retention provided by the study team. The study team, which includes the study biostatistician, has selected the randomization approach "*Varying (flexible) randomization ratio (1:1, 2:1, 3:1)*" described below based on changes in expected retention and power calculations also described below.

The original statistical power consideration was based on 1:1 randomization to treatment and control. Assuming 70% retention rate, 448 caregivers at the end of the study will allow us to detect an effect size of 0.265 in the primary outcome PHQ-8 depression symptoms score with a power of 0.80 at a significance level of 0.05 (two-sided). The effect size of 0.265 corresponds to about 1.5 difference in PHQ-8 score (range 0-24) between groups assuming a common standard deviation of 5.6 (Lorig K, Thompson-Gallagher D, Traylor L, et al. Building Better Caregivers: a pilot online support workshop for family caregivers of cognitively impaired adults. *Journal of Applied Gerontology*. 2012;31:423-437.)

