If enough caregivers are enrolled in a 2-week period (e.g., 54) to use a 1:1 randomization, that will be used; if there are somewhat fewer (e.g., 41), 2:1 randomization will be used; if fewer (e.g., 36), 3:1 randomization will be used. Use of this flexible approach has achieved high retention rates in the prior trials (e.g., Lorig KR, Sobel DS, Stewart AL, et al. Evidence suggesting that a chronic disease self-management program can improve health status while reducing hospitalization: a randomized trial. *Medical care* 1999;37:5-14). Assuming that the

randomization with varied ratios will increase the retention rate from 50% to 75% and the randomization ratio will be controlled for as a categorical variable in the analysis model, 480 caregivers at the end of the study will allow us to detect a partial correlation of 0.13 between the treatment and outcome with a power of 0.82 at a significance level of 0.05 (two-sided).

Randomization plan	Total sample size	Retention rate	# participants at the end of the study	Power	Effect size
Original 1:1	640	70%	448	0.80	0.265 (a treatment group difference of 1.5 in PHQ-8 score)
Original 1:1 but with revised downward estimate of retention based on new information from VA	640	50%	320	0.63	0.265
Fixed 2:1	640	75%	480	0.78	0.265
Fixed 3:1	640	75%	480	0.71	0.265
Varying 1:1, 2:1, 3:1	640	75%	480	0.82	A partial correlation of 0.13 between treatment and PHQ-8 score.

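### The primary model omits the randomisation ratio that the power memo promises to control for, and a ratio main effect alone would not adjust the group-by-time test

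*Combined protocol and SAP*

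**What the plan says.** The Protocol document is a power memo dated August 2019. It states: "The study team, which includes the study biostatistician, has selected the randomization approach" in which the allocation ratio varies. The ratio follows from how many caregivers enrol in a 2-week period: with about 54 it is 1:1, and "if there are somewhat fewer (e.g., 41), 2:1 randomization will be used; if fewer (e.g., 36), 3:1 randomization will be used". For this design the memo assumes 75% retention (480 of 640), says that "the randomization ratio will be controlled for as a categorical variable in the analysis model", and on that basis expects to "detect a partial correlation of 0.13 between the treatment and outcome with a power of 0.82".

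Section 8.26 of the Combined protocol and SAP (Primary analyses) fits linear mixed models to stress and PHQ-8, with group, time and group-by-time "interaction terms as fixed effects and community organizations and subjects as random effects". The test is specified in these words: "interaction term will be used to evaluate if the two groups differ in outcomes over time". The only route for any other covariate is this rule: "Covariates with imbalanced distributions between the two groups will also be included in the models to control for potential confounding". Neither randomisation ratio nor recruitment period is named.

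The rest of the application describes the earlier design. Sections 4.1, 8.3 and 10.1 give 320 per arm. Section 8.26 says "The study is powered to allow 30% loss to follow up", and section 10.3 expects 448 completers, 224 per group.

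**The concern.** The two documents describe different designs and different models for the same primary test. The likely reason is that the application was not updated after the memo; nothing in it argues against adjustment. An analyst who follows 8.26 as written would still leave out an adjustment that the memo's power figure assumes.

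The obvious repair also falls short. Under the varying ratio, the two arms draw on the ratio strata in different proportions. If 12-month change differs between strata, for instance because slow-recruiting periods differ from fast ones, some of that difference is read as a treatment effect. The tested term is a difference in change. A covariate that is fixed within a caregiver shifts every visit equally and drops out of change. Copying the memo's sentence into 8.26 as a main effect would therefore appear to adjust the primary test without doing so. Neither document mentions ratio by time.

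**Working it through.** **Inputs from the documents.** N = 480 completers; PHQ-8 SD 5.6; target 1.5 points (effect size 0.265); two-sided 0.05; example period sizes 54, 41 and 36; visits at baseline, 1.5, 6 and 12 months.

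**Assumed, because the documents do not give them.** The mix of ratios; the difference D in 12-month change between the 1:1 and 3:1 strata, with 2:1 midway; within-caregiver correlation rho = 0.6.

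**Reproducing the plan's power.** With noncentrality 0.265 × √(N·p(1−p)), where p is the treated proportion, the noncentral t gives 0.80 for 1:1 at N = 448, 0.78 for 2:1 and 0.71 for 3:1 at N = 480. All three match the memo. A noncentral F test of a partial correlation of 0.13 at N = 480 gives 0.818, against the stated 0.82.

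**Stratum shares at the memo's period sizes.** I read 54, 41 and 36 as 27/27, 27/14 and 27/9 (treated/control), with equal numbers of periods of each kind.
- Treated: 27/81 = 33% from each stratum.
- Controls: 27/50, 14/50 and 9/50 = 54%, 28% and 18%.
- Of 640 caregivers, 640 × 81/131 ≈ 396 are treated and 244 are controls, not 320/320.

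**Bias in group-by-time without adjustment.** Bias = D × Σ(treated share − control share) × (0, 0.5, 1). At the memo's sizes this is D × [(0.333 − 0.280) × 0.5 + (0.333 − 0.180) × 1] = 0.18 D.

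**False-positive rate.** SE of the difference in change = √(2 × 5.6² × (1 − rho) / (480 × p̄(1 − p̄))), where p̄ is the overall treated proportion. At the memo's sizes p̄(1 − p̄) = 0.236, so SE = √(25.088/113.3) = 0.471. A bias of 0.18 then gives 6.7% by normal approximation.

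**Cost of adjustment.** SE ratio = √(p̄(1 − p̄) / Σw·p(1 − p)), where w is the share of caregivers in each stratum. Power uses noncentrality 0.265 × √(480·I), with I = p̄(1 − p̄) unadjusted and I = Σw·p(1 − p) adjusted.

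| Mix of ratios | Bias at D = 1 (share of 1.5) | False positives at D = 1 | Power, unadjusted → adjusted | Effect size equal to r = 0.13 |
|---|---|---|---|---|
| Equal thirds | 0.18 (12%) | 6.7% | 0.795 → 0.776 | 0.280 |
| Memo period sizes | 0.18 (12%) | 6.7% | 0.804 → 0.785 | 0.276 |
| Half 1:1, half 3:1 | 0.27 (18%) | 8.7% | 0.801 → 0.773 | 0.280 |
| 80/15/5% | 0.08 (5%) | 5.4% | 0.824 → 0.814 | 0.266 |
| 10/80/10% | 0.06 (4%) | 5.2% | 0.785 → 0.779 | 0.279 |
| Half 2:1, half 3:1 | 0.05 (3%) | 5.1% | 0.750 → 0.746 | 0.290 |

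The SE rises by 0.4% to 3.5%. At D = 0.5 every mix gives 5.0% to 5.9% false positives. With a single ratio throughout there is no bias. The last column is 0.13/√(1 − 0.13²)/√I, with I adjusted.

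**Does a main effect help?** Simulations with no true treatment effect, four visits and equal thirds gave these results for the 12-month group-by-time estimate at D = 1 (1,500 replicates):

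| Data | No ratio term | Ratio main effect | Ratio by time |
|---|---|---|---|
| 480, complete: bias; false positives | 0.187; 7.0% | 0.187; 7.0% | 0.012; 4.9% |
| 640, 25% dropout: bias; false positives | 0.181; 6.7% | 0.181; 6.5% | 0.002; 4.5% |

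A separate mixed-model simulation with D = 2 and 640 caregivers (60 replicates, Monte Carlo SE about 0.06) gave 0.381, 0.381 and 0.038 with complete data, and 0.380, 0.379 and 0.005 with 25% dropout. A difference between strata in level only produced no bias in group-by-time under any model. At the memo's period sizes (12-month change, 4,000 replicates), D = 2 gave a bias of 0.34 and 11.2% false positives without ratio, against −0.01 and 5.2% with ratio by time.

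**The case against.** The strongest reply is that the adjustment is already promised. The memo says ratio will be controlled for, 8.26 is only a brief summary, and the application still lists its registration number as pending, so this is a matter of synchronising documents. Neither document restricts ratio to a main effect, and ratio could be caught by the imbalanced-covariate rule. That is fair as to intent. But the form of the adjustment is left open, the rule depends on the data and does not name ratio, and the plain reading of both texts adds a main effect.

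The cancellation also depends on baseline being one of the modelled visits. Section 8.26 does not say so outright, though the visit schedule and the group-by-time test imply it. Section 8.4 places the main comparison at 12 months. If that means the group difference at 12 months rather than the difference in change, a ratio main effect does help. At the memo's sizes and rho 0.6, a level-only difference of 1 point biases that contrast by 0.18 without ratio and 0.00 with a main effect; a 1-point difference in change gives 0.17 and 0.10. This stands as a limit on the cancellation argument. It also opens a second route to bias, which ratio plus ratio by time would cover as well.

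Finally, the harm is hypothetical. No passage links enrolment volume to PHQ-8 change, and a 1-point difference is two-thirds of the treatment target. False-positive rates stay near nominal in three of the six mixes. The rate also depends on rho: at the memo's sizes and D = 1 it is 6.0%, 6.7% and 8.4% for rho of 0.3, 0.6 and 0.8. Adjustment takes power below 0.80 in two mixes. All of this is correct and limits the point to one that should be fixed, without any claim of demonstrated bias.

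**Conclusion.** The concern holds. Two parts are unconditional: 8.26 omits a term that the memo says the model will contain, and a ratio main effect cancels from the group-by-time test when baseline is a modelled visit (exactly with complete data, almost exactly with dropout).

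The bias is conditional on 12-month change differing between ratio strata. There is none in group-by-time if strata differ only in level, and none is expected if period effects are unrelated to ratio. Given such a difference, 5% to 27% of it enters the PHQ-8 estimate over the mixes tried. The same fractions apply to the stress score, but no false-positive rate can be given there because the documents state no stress SD. The case for acting is that the team has already committed to the adjustment, it is cheap, and fixing its form in advance removes a choice between models after the data are seen.

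**What to change.** - **Section 8.26:** name randomisation ratio (three levels) and ratio by time as fixed effects in the primary PHQ-8 and stress models. Carry both into the secondary models where the data support it; this was not computed for categorical or count outcomes. State whether the tested contrast is the difference in change or the 12-month difference, so that 8.4 and 8.26 agree.
- **Sections 4.1, 8.3 and 10.1:** replace 320/320 with the memo's flexible allocation.
- **Sections 8.26 and 10.3, together:** replace 30% loss, 448 completers, 224 per group and power 0.8 with 75% retention, 480 completers and a power computed for the flexible allocation at effect size 0.265. Do not carry over the memo's 0.82 for this. It belongs to a partial correlation of 0.13, which equals an effect size of 0.266 to 0.290 in the mixes above.

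**Cost:** wording, and up to 8 model degrees of freedom (2 for ratio, 2 × 3 = 6 for ratio by time with four visits). Power at 0.265 falls by 0.004 to 0.028, for example from 0.804 to 0.785 at the memo's period sizes. On the change-score SE (rho 0.6, 1.5 points), equal thirds goes from 0.883 to 0.868.

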**For Aim 1-Procedures for RCT.**

Only #1 below will be done if a potential participant does not enroll in the study.

1. **Eligibility:** Eligibility will be determined by an anonymous online screening survey. Potential participants will also be given the option to complete it by mail or phone, if they prefer. Potential participants will be asked their age, gender, to indicate the outreach effort(s) they are responding to in which targeted rural communities, followed by the eligibility criteria: caring for patient with dementia (PWD); able to read and write in English; able to access the internet; providing care for  $\geq 10$  hours per week.

2. **Informed consent:** After confirming eligibility they will read all consent forms (written at the 6th grade level) online. These will be formatted so that they can print them out if desired. They will be offered the opportunity to discuss the study by email or phone with the study coordinator or PI. Those comfortable doing so will then complete the online consent form (or a mailed hardcopy, if they prefer).

3. **Randomization.** Caregivers will be randomized after completion of enrollment and the baseline survey (see4a). Staff will inform study participants about treatment assignment by e-mail or telephone (according to caregiver preference). Caregivers will be randomized to 6-week intervention or attention control group.

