#### 4. **Activities by group:**

a. **Intervention group.** Participants will receive the Building Better Caregivers workshop. Building Better Caregivers is an online 6-week, interactive, small-group self-management, social support, and skills-building workshop developed for caregivers of individuals with Alzheimer's disease or related forms of dementia. Workshop content encompasses two complementary categories—topics that address caregiver self-management and topics that focus on dementia caregiving skills. Workshops consist of 20-25 persons. Each week, participants are asked to log on at least 2-3 times for a total time of approximately two hours. Activities are guided by two peer co-facilitators (caregivers themselves). Caregiver participation does not require "real time" attendance at pre-determined times. Caregivers interact in group discussions and person-to-person communications by making postings on discussion boards and sending individual messages. They can write these at any time of day or night. Such participant interactions are frequent and similar to email, Facebook, or texting exchanges. Each week focuses on the introduction of 2-3 new topics, with some key topics repeated in subsequent weeks. Lessons are then reinforced in the Discussion Center section of the website, where the peer social support occurs.

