b. **Attention control group.** Participants will receive written materials on dementia and caregiver resources and two brief phone calls of 15-30 minutes apiece by research staff. Caregivers in the attention control group will be offered the online workshop after the 12 month trial is completed if they so desire. The written materials and phone call guides are still under development and will be submitted to the IRB for review as a modification request.

**For control group fidelity purposes.** Phone calls will be recorded. [name] and the research coordinator will evaluate recordings using a fidelity assessment instrument. Staff who stray from the phone call protocol will receive immediate remedial training. If an RA strays from the protocol again, he/she will be removed from making phone calls. At the outset of the trial, fidelity assessment will occur approximately every 4-5 calls to assure fidelity patterns are quickly established and reinforced. Subsequent checks will occur every 10-12 calls.

5. **Assessments:** Data will be collected at baseline, 1.5 months (post intervention), 6 months, and 12 months. Data will be collected through online surveys completed by caregivers and conducted at baseline, post-intervention (1.5 months), and 6, and 12 months using the secure REDCap application. Assessments are expected to be 20 minutes each. Participants will be given the option to complete surveys by mail or phone interview.

a. **Baseline** questions will ask about caregiver and PWD demographic information (e.g., age, gender, race/ethnicity, education); caregiving relationship to PWD (e.g., spouse, child), and resources participants are accessing (e.g., paid in-home care). Baseline questions also will identify caregiver and partner chronic conditions (e.g., using the Charlson comorbidity index), partner need for assistance with ADLs and IADLs, and dementia characteristics (e.g., diagnosis, length of diagnosis, degree of impairment, presence of behavioral symptoms). Caregiver (CG) stress level (Stress visual numeric scale), CG depression symptoms (PHQ-8 score), Self-efficacy (Revised Scale for Caregiver Self-efficacy), Burden (Zarit Burden Inventory), Strain (Caregiver Strain Index), Global health score, and Healthcare utilization items.

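### Intervention caregivers are treated in interacting workshops, but neither the primary models nor the stated powers allow for correlation within workshop

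*Combined protocol and SAP*

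**What the plan says.** **Delivery.** Section 8.10, item 4a (Combined protocol and SAP): "Workshops consist of 20-25 persons". Each workshop has two peer co-facilitators and runs for six weeks. "Caregivers interact in group discussions and person-to-person communications by making postings on discussion boards and sending individual messages". "Lessons are then reinforced in the Discussion Center section of the website, where the peer social support occurs". For controls, item 4b says: "Participants will receive written materials on dementia and caregiver resources and two brief phone calls of 15-30 minutes apiece by research staff". Only one arm is grouped, so the design is partially nested.

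**Timing.** Section 8.10, item 3: "Caregivers will be randomized after completion of enrollment and the baseline survey". A workshop effect can therefore start only after baseline.

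**Analysis.** Section 8.26 gives fixed effects for group, time and their interaction, and the random part is "community organizations and subjects as random effects to account for the correlation within organizations and subjects due to measurements over time". The secondary models are described as similar. The power memo adds randomization ratio as a categorical covariate. No passage gives a workshop term, a workshop ICC, a design effect or a cluster-robust variance.

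**Power.** Section 10.3 and the memo state 0.80 (1:1, 448 completers), 0.78 (fixed 2:1, 480), 0.71 (fixed 3:1, 480) and 0.82 (varying ratio, 480, partial correlation 0.13).

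**The concern.** Some correlation within workshop is plausible on the plan's own account: peer support is said to arise in the shared discussion area, and section 8.26 lists social support among the possible treatment pathways.

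The planned random effects do not cover it:

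- **Organization.** The memo describes filling workshops from 2-week recruitment windows, and no passage maps organizations to workshops. Both arms share the organization effect, so it cannot represent an effect that exists only in the intervention arm.
- **Subject.** This handles repeated measures on one person. It does not handle correlation between different people in the same workshop after baseline, and that correlation falls on the group-by-time contrast.

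If the correlation is there, confidence intervals for both co-primary outcomes are too narrow and a test that respects the design has less power than stated. The error is in the anti-conservative direction.

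**Working it through.** **Inputs from the documents**
- Effect size d = 0.265, two-sided alpha 0.05, 224 completers per group at 70% retention (section 10.3).
- 320/160 and 360/120 completers at 75% retention; partial correlation r = 0.13 with 480 completers (power memo).
- Workshop size 20 to 25 (section 8.10). The memo's example intakes imply about 27: 54 × 1/2 = 27, 41 × 2/3 = 27.3, 36 × 3/4 = 27.

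**Assumptions**
- ICC 0.01 to 0.05, because the documents give none.
- A 12-month completer comparison stands in for the group-by-time test.
- Completers per workshop, m = size × retention: 14 to 17.5 at 70%, 15 to 18.75 at 75%.

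**Step 1. Reproduce the stated powers with independent participants.** With v0 = 1/n1 + 1/n2, power = Φ(d/√v0 − 1.96).
- 224/224: √v0 = 0.0945; Φ(2.80 − 1.96) = 0.80 (stated 0.80).
- 320/160: √v0 = 0.0968; Φ(2.74 − 1.96) = 0.78 (stated 0.78).
- 360/120: √v0 = 0.1054; Φ(2.51 − 1.96) = 0.71 (stated 0.71).
- Varying: r/√(1 − r²) × √480 = 0.1311 × 21.91 = 2.87; Φ(2.87 − 1.96) = 0.82 (stated 0.82).

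All four match, so none holds an allowance for workshop.

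**Step 2. Let the intervention arm be clustered.**
- Design effect DE = 1 + (m − 1) × ICC, in the intervention arm only.
- v = DE/n1 + 1/n2; SE ratio = √(v/v0).
- Type I error of a test that ignores workshop = 2[1 − Φ(1.96/ratio)].
- Large-sample power of a test that allows for workshop = Φ(d/√v − 1.96).
- Satterthwaite: a = DE/n1, b = 1/n2, k = n1/m workshops, df = (a + b)²/[a²/(k − 1) + b²/(n2 − 1)]; power from the noncentral t with noncentrality d/√v.

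Example, 1:1, m = 17.5, ICC 0.05: DE = 1 + 16.5 × 0.05 = 1.825. v = 2.825/224 = 0.01261, so √v = 0.1123 and the ratio is 0.1123/0.0945 = 1.19. Type I error = 2[1 − Φ(1.65)] = 9.9%. Large-sample power = Φ(2.36 − 1.96) = 0.66. Satterthwaite df = 27.8 and power 0.62.

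**Step 3. The varying plan.** The mix of ratios is not stated, so completers under 1:1, 2:1 and 3:1 are assumed to run from 400/40/40 to 40/40/400. With p = 1/2, 2/3, 3/4 and q = 1 − p:
- stratum weights w are proportional to npq, and v = Σw²[DE/(np) + 1/(nq)];
- d = 0.1311 × √(480/Σnpq). Σnpq is 116.4 and 93.9 for the two mixes, so d = 0.266 and 0.296;
- component df are workshops − 3 and controls − 3.

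**Results.** Low end is 20 per workshop with ICC 0.01; high end is 25 per workshop with ICC 0.05.

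| Plan | End | SE ratio | Type I if ignored | Power, large-sample | Power, Satterthwaite (df) | Stated |
|---|---|---|---|---|---|---|
| 1:1, 448 | low | 1.03 | 5.8% | 0.78 | 0.76 (50.6) | 0.80 |
| | high | 1.19 | 9.9% | 0.66 | 0.62 (27.8) | |
| 2:1, 480 | low | 1.02 | 5.5% | 0.76 | 0.76 (110.7) | 0.78 |
| | high | 1.14 | 8.5% | 0.67 | 0.66 (61.2) | |
| 3:1, 480 | low | 1.02 | 5.4% | 0.70 | 0.69 (129.7) | 0.71 |
| | high | 1.11 | 7.6% | 0.62 | 0.61 (88.0) | |
| Varying, mostly 1:1 | low | 1.03 | 5.8% | 0.79 | 0.78 (52.3) | 0.82 |
| | high | 1.19 | 10.0% | 0.67 | 0.64 (26.7) | |
| Varying, mostly 3:1 | low | 1.02 | 5.5% | 0.80 | 0.80 (118.1) | 0.82 |
| | high | 1.12 | 8.0% | 0.73 | 0.72 (69.6) | |

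With 27 per workshop at 1:1 (m = 18.9), type I error is 6.0% to 10.3% and Satterthwaite power 0.74 to 0.61.

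**Step 4. Simulation check.** Change scores at 12 months with a post-baseline workshop effect, analysed ignoring workshop, gave type I errors of about 6.8% at ICC 0.02 and 9.0% at ICC 0.05 (1:1, about 16 completers per workshop). This agrees with the formula.

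**The case against.** The case on the other side concerns size, and much of it stands.

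- **Narrower null.** Caregivers are individually randomized. If the workshop affects nobody, sharing one adds no correlation and the ordinary test stays approximately valid. The type I figures apply only where the average effect is zero but workshops still differ, or members influence one another with no net effect. This stands as a limit. Whether to allow for workshop is also partly a choice between inference to these workshops and to workshops in general; the scalability aim in section 4.1 favours the second.
- **Probably a low ICC at 12 months.** The main comparison comes about 10.5 months after a six-week, asynchronous programme. Non-attenders kept under intention to treat dilute the correlation, and facilitator training with weekly fidelity review may limit it further. This is reasonable but unquantified.
- **Proxy calculation.** The planned model uses four visits and all available data. Baseline correlation could raise power, but could also raise workshop's share of the remaining variance. The net direction is unknown.
- **Document type.** Section 8.26 is a form field that asks for a brief summary, and the memo answers a question about drop-out. Even so, 8.26 does name its random effects and already models organization.
- **Few workshops.** The workshop variance may be estimated at or near zero. By the formula above, Satterthwaite power at 1:1 is about 0.79 even at ICC 0. A prespecified sensitivity analysis would be a defensible lesser remedy.

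None of these points to text that covers workshop correlation. An unknown ICC is no reason to fix it at zero.

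**Conclusion.** The concern holds, in conditional form, and should be fixed. The omission is certain: no model term or power figure allows for workshop. It touches both co-primary outcomes, the analogous secondary models and the selected varying-ratio plan. How much harm follows is illustrative, since it depends on an assumed ICC, a completer comparison and, for the varying plan, an assumed mix of ratios. At ICC 0.01 the effect is minor, with type I error at most about 6%. At ICC 0.05 and 1:1, type I error roughly doubles and Satterthwaite power falls by about 18 points (0.80 to 0.62). At ICC zero the planned analysis is not harmed.

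**What to change.** 1. Carry the assigned workshop into the analysis data. The platform records workshop interactions, so membership is probably recoverable.
2. Add to both primary models, and to the analogous secondary models, a workshop random effect that acts only in the intervention arm and only at post-baseline visits.
3. Use Satterthwaite or Kenward-Roger degrees of freedom in the linear models. With 640 × intervention share divided by 27 to 20 per workshop, there will be only about 12 to 16 workshops at 1:1, 16 to 21 at 2:1, 18 to 24 at 3:1, and 13 to 23 under the varying plan, depending on the mix.
4. Reconcile the workshop size (20 to 25 in section 8.10, about 27 implied by the memo). Then restate power over a stated ICC range and a stated mix of ratios, using those degrees of freedom.

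The cost is analysis-plan wording, one extra variable and a recomputed power table. The downside is somewhat wider intervals, a lower stated power, and a workshop variance that is estimated imprecisely from so few workshops.
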